With our initial 10 patients we are able to report that in all 10 patients the images were successfully required. We then performed an analysis of the 20 total cerebral hemispheres (right and left). Nineteen of 20 hemispheres demonstrated a significant change in CBF perfusion in response to Diamox ($p<0.05$). Six hemispheres demonstrated a 30% change in CBF and 12 had a 15% change. In 9 hemispheres there was the expected increase in CBF in response to Diamox. In 10 hemispheres there was a decrease in CBF. There was no statistical difference in the percent change between left and right hemispheres which would correlate with the global vasodilatory effects of Diamox. Symptomatic vasospasm then only developed in 2 of our patients. In one of these patients there was a pathological decrease in CBF in response to Diamox while the other had an appropriate increase in CBF. The goal of the analysis in this extension of the study is to better understand the changes in CBF in patients that go on to develop symptomatic or clinical vasospasm based on a change in neurological exam. Unfortunately, in our first phase of the pilot study only 2 patients developed symptomatic vasospasm. The reason we are requesting an extension to 30 patients is so we can capture a

larger number of patients with symptomatic vasospasm. Then we can assess our statistical analysis to see if we can consistently see a significant lack of response (either <30% increase in CBF or a decrease in CBF) to Diamox. With only 2 patients in our initial cohort developing symptomatic vasospasm it is impossible to make a more robust statistical proposal and that is why we are submitting a request to study more cases.

As discussed before, in this study design there is no need for a control group. We are comparing our CBCT information to the conventional method which is the clinical neurological exam change which indicates clinical or symptomatic vasospasm. The data that will be statistically compared is the pre-diamox perfusion in comparison to the post-diamox perfusion. A statistically significant change increase in CBF represents an appropriate response to Diamox. Lack of change in CBF or decrease in CBF could be suggestive of potential for developing vasospasm. More data with patients who develop clinical vasospasm is needed in order to correlate these changes with this subset of patients.

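### The plan gives two incompatible criteria for an adequate CBF response to acetazolamide, so a significant increase below 30% is labelled both abnormal and appropriate

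*Combined protocol and SAP*

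**What the plan says.** Three sentences in the IRB Concerns section bear on what counts as an abnormal response.

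- On the purpose of the extension, the plan wants to see whether patients with symptomatic vasospasm regularly show a "significant lack of response (either <30% increase in CBF or a decrease in CBF) to Diamox". This is a criterion of size: 30% or more is adequate, anything less is not.
- The next paragraph says "A statistically significant change increase in CBF represents an appropriate response to Diamox". This is a criterion of significance, with no size attached.
- It continues: "Lack of change in CBF or decrease in CBF could be suggestive of potential for developing vasospasm". A small but real increase is not on this list.

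The same section defines the test: a paired t-test on 40 matched slices per hemisphere, before and after the drug, at p<0.05.

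The pilot results come as hemisphere counts. On significance, the plan reports: "Nineteen of 20 hemispheres demonstrated a significant change in CBF perfusion in response to Diamox". On size, without giving direction, it reports: "Six hemispheres demonstrated a 30% change in CBF and 12 had a 15% change". On direction, it reports 10 decreases and describes the rest this way: "In 9 hemispheres there was the expected increase in CBF in response to Diamox". For the outcome, it says: "Symptomatic vasospasm then only developed in 2 of our patients". One of these had a decrease, "while the other had an appropriate increase in CBF".

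The Statistical Considerations section states the aim of the extension as correlating percent change in CBF with later vasospasm. It names no cut-off.

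**The concern.** An increase of, say, 15% that passes the t-test is a lack of response under the first sentence and an appropriate response under the second. The two criteria agree on decreases. They disagree on significant increases below 30%, and nothing in the readable text ranks them or requires both.

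At stake is the extension's question of whether patients who develop vasospasm consistently lack a response. The same hemisphere can count for or against that pattern, depending on the sentence applied. Few vasospasm cases are likely, given 2 among the first 10 patients. If the label is settled only after outcomes are known, the choice could shape the conclusion. The protocol also presents the scan as a possible screening tool, and that use needs one definition of an abnormal test.

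**Working it through.** **Inputs, all from the IRB Concerns section.** 10 pilot patients, 20 hemispheres; 19 with a significant change; 9 increases; 10 decreases; 6 hemispheres with a 30% change, direction not given; 40 paired slices per test; p<0.05.

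**Step 1: reproduce the plan's count.** 9 + 10 = 19, which matches the 19 of 20 reported as significant. Only 19 hemispheres are given a direction. I therefore take the 9 increases as significant and the twentieth hemisphere as the non-significant one. This is an inference, not a statement in the plan.

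**Step 2: significance criterion.** Appropriate = 9. Abnormal = 20 − 9 = 11 of 20 (10 decreases plus the non-significant hemisphere).

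**Step 3: 30% criterion.** Read a 30% change as at least 30% in either direction. Let k be the number of increases that reached 30%. Only six hemispheres changed by that much, so k lies between 0 (all six were decreases) and 6 (all six were increases).

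- Abnormal = 20 − k, so 14 to 20 of 20.
- Increases labelled in opposite ways = 9 − k, so 3 to 9 of 20 (15% to 45%).

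| k | Abnormal, 30% criterion | Abnormal, significance criterion | Opposite labels |
|---|---|---|---|
| 0 | 20 | 11 | 9 |
| 3 | 17 | 11 | 6 |
| 6 | 14 | 11 | 3 |

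Whether the 12 hemispheres with a 15% change include the six does not alter this range. If one of the 9 increases were the non-significant hemisphere, 8 significant increases would remain and the range would be 2 to 8, still not empty.

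**Step 4: does the t-test imply a size?** No. With 40 pairs treated as independent and a two-sided test (the plan does not state sidedness), the critical value is t(0.975, 39 df) = 2.0227. A mean change is significant once it exceeds 2.0227/√40 = 0.32 SD of the slice differences. That SD is not given, so the threshold cannot be turned into a percent. It depends on variation between slices and not on any chosen minimum change in CBF.

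**Step 5: the two vasospasm patients.** One had a decrease and the other an increase of unstated size. No readable rule says how two hemispheres make one patient result. Their classification under the two criteria cannot be worked out.

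**The case against.** The strongest reply is that neither statement is offered as a decision rule. The 30% sentence poses a question, and the later sentence says only that a pattern might point to vasospasm. The significance criterion has to be assembled from two sentences, of which only one mentions significance. A charitable reader could split the roles, with the t-test showing that the drug did something and 30% being the size looked for in patients with vasospasm. The stated aim is a correlation on percent change, which needs no label. Under Scan procedure, the images are not used for clinical decisions. The section also refers to slides on the statistics that are not shown.

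Much of this stands. It limits the consequence to an exploratory label, and the slides may hold a ranking. It does not remove the conflict: the text never states the split of roles, and it calls one kind of result by two opposite names in adjoining paragraphs.

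A reader might infer more than the documents support:

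- That the pilot already shows a changed result, with one vasospasm patient missed by one criterion and detected by the other. The size of that patient's increase is not given, and neither is the step from hemispheres to patient. If the increase reached 30% in both hemispheres, the criteria would agree.
- That the main correlation is compromised. It uses percent change directly and is unaffected.

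**Conclusion.** The conflict is real and minor. The plan holds two stated criteria that label a significant increase below 30% in opposite ways, and the readable text does not choose between them. In the pilot, 3 to 9 of 20 hemispheres are in dispute: 11 of 20 abnormal by significance against 14 to 20 of 20 by the 30% cut-off.

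The range assumes that a 30% change means at least 30% in either direction and that all 9 increases were significant. What is affected is the exploratory question of a consistent lack of response. The documents do not show that either pilot vasospasm patient would be reclassified. Nor do they show that 30% is the better criterion, since no readable text justifies that figure. Because the slides are not shown, the finding is a conflict of wording in the readable text and not proof that no ranking exists.

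**What to change.** - Keep percent change in CBF, as a continuous variable, as the main predictor of vasospasm, as Statistical Considerations already intends.
- Do not use the 40-slice p<0.05 test to label a response, because it sets no minimum size of change.
- Reconcile the three sentences in IRB Concerns into one size-based definition, with a cut-off that the investigators choose and justify.
- Add a rule for turning two hemispheres into one patient result.
- Fix both before the new patients' maps are linked to outcome, and report any dichotomous result as exploratory beside the continuous analysis.
- If the slides already hold a rule, state it in the text.

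The cost is a few sentences and no new data. The downside is that the investigators must commit to a cut-off in advance with little to go on: the readable text gives no justification for 30%, and the pilot has only 2 vasospasm patients.

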We propose a technique using cone beam perfusion (CBCTP) with an acetazolamide challenge as a potential diagnostic tool to detect a defect in cerebral autoregulation at a time when it has not yet caused clinically apparent signs or symptoms. Acetazolamide is a carbonic anhydrase inhibitor which works to increase the arterial concentrations of carbon dioxide. Carbon dioxide is an important regulator of cerebral vasculature and serves as a potent vasodilator. Acetazolamide or vasodilatory challenge should identify subjects having an abnormal cerebrovascular reactivity capacity. More specifically, after receiving the drug there will not be the expected increase CBF in some of the subjects because they are already suffering from a disturbance in the vasculature's ability to respond to the signal for vasodilation. We ultimately believe the presence of this deficit will be helpful in identifying patients who are at risk for potential brain ischemia due to this decreased capacity to autoregulate if/when clinically significant vasospasm occurs. We predict that acetazolamide-activated regional cerebral blood flow studies will be more sensitive in the detection of mild cerebral vasospasm and will not just detect changes in cerebral blood flow as does standard perfusion imaging, but will provide information regarding changes in cerebrovascular reactivity. Under these circumstances, we would have a better predictor of those patients at risk of cerebral infarction due to delayed vasospasm. Identifying this "high-risk cohort" prior to the onset of clinically apparent symptoms would result in the institution of preventative measures such as triple H therapy³.

Background and Significance

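### The under-30%-increase criterion labels 14 to 20 of the 20 pilot hemispheres abnormal, and the stated check has no comparison with patients without vasospasm, so a consistent result in cases would not show prediction

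*Combined protocol and SAP*

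**What the plan says.** All places are in the combined protocol and SAP.

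- **Criterion.** IRB Concerns describes what the extension will look for in patients with symptomatic vasospasm: a "lack of response (either <30% increase in CBF or a decrease in CBF) to Diamox", seen consistently. The same section argues that no control group is required.
- **Second definition.** The next paragraph of that section treats any statistically significant rise in CBF as an appropriate response, and no change or a fall as suggestive of later vasospasm. It sets no 30% threshold.
- **Pilot hemispheres.** "Nineteen of 20 hemispheres demonstrated a significant change in CBF perfusion in response to Diamox". "In 9 hemispheres there was the expected increase in CBF in response to Diamox". "In 10 hemispheres there was a decrease in CBF". "Six hemispheres demonstrated a 30% change in CBF and 12 had a 15% change". No direction is given for the last two counts.
- **Pilot outcome.** "Symptomatic vasospasm then only developed in 2 of our patients": one with a fall in CBF, the other with a rise described as appropriate, size not stated.
- **Aim.** Statistical Considerations and the closing text of IRB Concerns name a correlation between percent change in CBF and later vasospasm as the purpose of the extension. Study Objective speaks of a screening tool, and the opening section of identifying high-risk patients before symptoms appear.

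**The concern.** A predictive criterion has to separate patients who develop vasospasm from those who do not. The pilot counts suggest that this one places most hemispheres on the abnormal side whatever the outcome. If so, most vasospasm patients will show a lack of response simply because most patients do. The check described looks only at cases, so it has no means of exposing this. At stake is the interpretation of the extension: an apparently consistent finding in cases could be taken as support for a screening use, and the Data and Safety Monitoring Plan says a formal study will be proposed if the pilot validates the technique.

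**Working it through.** **Inputs** (all from IRB Concerns): 20 hemispheres from 10 patients; 19 with a significant change; 9 rises; 10 falls; 6 with a 30% change; 2 patients with symptomatic vasospasm. Assumption: a 30% change means at least 30%. Whether the 12 hemispheres with a 15% change include these six does not affect the bounds.

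**1. The plan's own tally.** 9 + 10 = 19 significant changes, and 19 + 1 non-significant = 20. The counts agree.

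**2. Hemispheres labelled abnormal.** Abnormal = 20 − (rises of at least 30%).

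- All six 30% changes were rises: 20 − 6 = 14 (70%).
- All six were falls: 20 − 0 = 20 (100%).
- Under the second definition (no significant rise): 20 − 9 = 11 (55%).

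The two definitions in one section therefore differ by 3 to 9 hemispheres out of 20.

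**3. Hemisphere-level performance.** The 2 cases contribute 4 hemispheres and the 8 non-cases 16. The base rate is 4/20 = 20%. The best case takes all six 30% changes as rises.

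| Case described as having an appropriate rise | Sensitivity | Specificity, at most | Positive predictive value, at most |
|---|---|---|---|
| Below 30% on both sides | 4/4 | 6/16 = 37.5% | 4/14 = 28.6% |
| At least 30% on both sides | 2/4 | 4/16 = 25% | 2/14 = 14.3% |

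Both rows take the other case as abnormal on both sides. The 37.5% ceiling holds wherever the responders fall, because there are never more than six of them.

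**4. Patient-level performance.** No aggregation rule is given, so I took two, counting every placement of 0 to 6 responding hemispheres and requiring the case with a fall to have at least one abnormal hemisphere.

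- *Either hemisphere abnormal flags the patient.* Six responders can clear at most 6/2 = 3 patients, so 7 to 10 of 10 are flagged. Specificity is 0 to 3/8 = 37.5%, and positive predictive value 1/9 = 11% to 2/7 = 29%.
- *Both hemispheres must be abnormal.* Six responders can clear up to 6 patients, so 4 to 10 of 10 are flagged. Specificity is 0 to 6/8 = 75%, and positive predictive value 0 to 2/4 = 50%.

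**5. Precision** (Clopper-Pearson 95% intervals). Vasospasm 2/10: 2.5% to 55.6%. Sensitivity 1/2: 1.3% to 98.7%; 2/2: 15.8% to 100%. Specificity 3/8: 8.5% to 75.5%; 6/8: 34.9% to 96.8%.

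**6. What a case-only check can show.** As an illustration, assume the pilot's 20% rate, giving 0.20 × 30 = 6 cases, and a flag unrelated to outcome.

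- 70% of patients flagged: expected flagged cases 0.70 × 6 = 4.2. P(at least 4 of 6) = 15(0.7⁴)(0.3²) + 6(0.7⁵)(0.3) + 0.7⁶ = 0.324 + 0.303 + 0.118 = 0.74.
- 85% flagged: 15(0.85⁴)(0.15²) + 6(0.85⁵)(0.15) + 0.85⁶ = 0.176 + 0.399 + 0.377 = 0.95.

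A useless flag would thus appear in most cases with probability 0.74 to 0.95 under these assumptions.

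**The case against.** The strongest reply is that the plan fixes no decision rule. The cut-off appears in parentheses, as something to examine, and the authors say two cases are too few for a firmer statistical proposal. They already name a correlation with percent change as the aim, and non-cases are available because patients are enrolled before the outcome is known. The scans do not guide care. One of the two cases had an appropriate rise, so the pilot itself does not report uniform non-response in cases. A test with high sensitivity and low specificity can also be useful for ruling out risk, and Background and Significance puts angiographic vasospasm at 30–70%, so a high rate of abnormal reactivity is not absurd in itself. Finally, figures are missing from the text available, and they may hold the signed results.

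Much of this stands, and it defeats a stronger reading. A reader might infer from 14 of 20 abnormal against 2 of 10 with vasospasm that the criterion cannot pick out a high-risk group. That comparison mixes hemispheres with patients. Like for like it is at least 14 of 20 hemispheres against 4 of 20, or 4 to 10 flagged patients against 2, depending on a rule the plan does not give. With two events, neither failure nor success can be claimed.

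The reply does not remove the gap in the analysis. The correlation aim is named but not specified. The only concrete criterion is a dichotomy examined in cases, with no stated comparison against non-cases.

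**Conclusion.** The concern holds in a limited form. On the plan's own counts the criterion labels 70% to 100% of pilot hemispheres abnormal, and hemisphere-level specificity in the pilot cannot exceed 37.5%. Both figures rest on reading a 30% change as at least 30%. Patient-level specificity could lie anywhere from 0 to 75% across the two aggregation rules tried, and sensitivity is nearly unknown. The documents therefore do not show that the criterion fails as a screen. They do show that consistent lack of response among cases, taken alone, would not be evidence of prediction, and that the section holds two definitions of a normal response which classify its own pilot data differently. It should be corrected before the extension data are analysed.

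**What to change.** 1. Make signed percent change in CBF the continuous predictor of symptomatic vasospasm across all 30 patients, for example by the area under the ROC curve with a confidence interval. This gives the correlation aim already in the plan a definite form.
2. State in advance one rule that reduces two hemispheres to one value per patient, such as the mean or the lower of the two.
3. Keep the 30% cut-off as a secondary, exploratory description. Report the proportion abnormal in patients with and without vasospasm, as sensitivity and specificity with confidence intervals. The comparators are the enrolled patients who do not develop vasospasm, so no separate control group is needed.
4. Reconcile the 30% criterion with the statistically-significant-rise definition in the same section.
5. Give the signed distribution for the first 10 patients, unless the figures already show it, and say that any cut-off drawn from these 30 patients is exploratory.

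The cost is analysis wording and some tabulation of values already planned; no further scans or patients are needed. The downside is that a single yes/no criterion is no longer the headline result. With few cases expected, the intervals will be wide, and the report should say so.

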All researchers and research staff involved in this project have completed Human Subjects and HIPAA training and are familiar with all procedures. The PI and co-investigators will review the data collected after the initial patients have been treated and outcome data becomes available. Adverse events or problems will be reviewed by the PI and co-investigators as they occur and will be reported to the IRB by the PI in accordance with posted guidelines. The PI and the co-investigators will meet regularly to review the data, adherence to the protocol and IRB guidelines. Data and safety monitoring will occur on a continuous basis by the research staff. The study team will meet regularly to review study progress including recruitment, data collection, and they will address any concerns or challenges that may arise. If initial pilot data shows that this technique is validated a formal study will be proposed to the IRB.

Statistical Considerations

The initial pilot study was conducted as a feasibility study and no robust statistical evaluation is possible. Since we have determined that the research imaging can be achieved safely and data reproducibly collected, we now hope to amend the cohort to a total of 30 patients so that we can capture more patients with vasospasm in order to have a more robust analysis of the correlation between percent change in CBF to Diamox and the future development of cerebral vasospasm.

IRB Concerns

The gold standard for determining if a patient has vasospasm is the clinical neurological exam. There is no currently accepted radiographic method or procedure for predicting vasospasm. Therefore, when comparing this proposed CBCT approach to the competing method we would be comparing it to the clinical neurological exam. Additionally, comparisons are being made to current methods of predicting vasospasm including TCDs, multidetector CTA/CTP, and angiography.

[figure not shown]
[figure not shown]

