The statistics that will be performed on the data maps are outlined in the images below. Using the perfusion map values, we will calculate relative percent change or improvement factor which is detailed in the slides below. When we say the results were reproducible it means that we were able to detect a change in perfusion in response to Diamox and that the maps were of good enough quality to be diagnostic. I have included examples below.

The statistical analysis on the relative percent change in CBF was a standard basic paired t-test. This test was performed in an identical manner for each hemisphere for each perfusion parameter map. For a given hemisphere and map test here were 40 slices of the image above the orbital line, a mean measurement was made for each slice location of the hemisphere. Thus, for pre and post Diamox we obtained 40 paired samples. From these paired samples (paired meaning they shared the same slice location pre and post Diamox) the paired-test was performed by taking the difference between all of the pre and post paired samples to obtain a set of 40 differences. From these 40 difference values one can get a mean and standard deviation to obtain the T statistic where a corresponding p-value can then be calculated. For our data set, we are selecting p-value of <0.05 as significant. We do not plan to use this data for a power analysis. Reproducibility has been established, but we are now aiming to draw correlations between patients with vasospasm and their CBF response to Diamox and that is the main aim of this expanded portion of the study.

References

3. Lee, K., et al. "Triple-H' Therapy for Cerebral Vasospasm Following Subarachnoid Hemorrhage." *Neurocritical Care*, vol. 4, no. 1, 2006, pp. 68-76.

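### The extension aims to relate CBF response to later vasospasm, but the only test named in the visible text compares CBF before and after acetazolamide, and two definitions of an abnormal response conflict

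*Combined protocol and SAP*

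**What the plan says.** Statistical Considerations justifies the extension by a firmer analysis of the "correlation between percent change in CBF to Diamox and the future development of cerebral vasospasm". The method text at the end of IRB Concerns says "we are now aiming to draw correlations between patients with vasospasm and their CBF response to Diamox and that is the main aim" of the expanded part.

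The analysis described is different. IRB Concerns states "The data that will be statistically compared is the pre-diamox perfusion in comparison to the post-diamox perfusion". It then says of the method: "The statistical analysis on the relative percent change in CBF was a standard basic paired t-test". That test takes 40 slice means per hemisphere, pairs them before and after the drug, and is run separately for each hemisphere and each perfusion map at p<0.05. For further detail the reader is referred to slides: "The statistics that will be performed on the data maps are outlined in the images below".

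The section names a change on the clinical neurological exam as the standard against which the imaging is judged. It words the goal as to "better understand the changes in CBF in patients that go on to develop symptomatic or clinical vasospasm", and adds: "More data with patients who develop clinical vasospasm is needed in order to correlate these changes with this subset of patients".

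It describes an abnormal response in two ways. One is a rise in CBF of less than 30%, or a fall. The other treats any statistically significant rise as normal, and no change or a fall as suspicious. Of the two pilot patients with symptomatic vasospasm, one had "a pathological decrease in CBF in response to Diamox while the other had an appropriate increase in CBF".

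**The concern.** The paired t-test asks whether CBF changed in one hemisphere of one patient. Vasospasm status is not an input, so no result of that test can say whether the change separates patients who later develop vasospasm from those who do not. That separation is the reason given for enrolling 20 more patients.

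Three things needed to bridge the gap are not visible: how two hemispheres become one patient result, which definition of abnormal applies, and which statistic links the result to vasospasm. If they are chosen after the data are seen, the apparent accuracy will partly reflect the choice.

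The goal is also worded around a consistent lack of response in patients with vasospasm. If that response is common in patients without vasospasm too, consistency in the first group alone says nothing about prediction.

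**Working it through.** **Inputs** (IRB Concerns unless stated): 10 pilot patients, 20 hemispheres; 19 with a significant change; 9 rises and 10 falls; 6 hemispheres with a 30% change and 12 with a 15% change, direction not given; symptomatic vasospasm in 2 patients; 40 slice pairs per test; total sample 30 (Study Methods). I read a 30% change as at least 30%, and the 9 rises and 10 falls as the 19 significant hemispheres. The tally agrees: 9 + 10 = 19. The sample size of 30 cannot be reproduced, because no effect size, power or precision target is given.

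**1. Room between the two definitions.** With 40 pairs, a two-sided test (sidedness is not stated, so assumed) is significant once the mean difference exceeds t(39)/√40 = 2.023/6.325 = 0.32 SD of the slice differences. If that SD were 10 or 30 percentage points (assumed), the threshold would be 3.2 or 9.6 points. Every rise between the threshold and 30% is normal under one definition and abnormal under the other.

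**2. Pilot hemispheres affected.** At most 6 hemispheres reached 30% in either direction, so at least 9 − 6 = 3 of the significant rises are below 30%. The definitions disagree on at least 3 of 20.
- Significant-rise definition: abnormal = 10 falls + 1 non-significant = 11/20.
- 30% definition: abnormal ≥ 20 − 6 = 14/20.

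**3. The hemisphere rule matters already.** Under the significant-rise definition 9 hemispheres are normal. Nine is odd, so at least one pilot patient has one normal and one abnormal hemisphere.

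**4. Patients without vasospasm, 30% definition.** The 2 vasospasm patients hold at most 4 of the 14 abnormal hemispheres, so at least 10 of the other 16 are abnormal.
- By hemisphere: specificity ≤ 6/16 = 37.5%.
- By patient, either hemisphere counts: 10 abnormal hemispheres at two per patient flag at least 5 of 8; specificity ≤ 3/8 = 37.5%.
- By patient, both must be abnormal: 10 over 8 patients leaves at least 2 with both; specificity ≤ 6/8 = 75%.

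**5. Pilot sensitivity.** If each vasospasm patient's two hemispheres agreed, it is 1/2 under the significant-rise definition: the fall is flagged, the rise is not. Under the 30% definition it is then 1/2 or 2/2, according to whether the rise reached 30%. The text does not say that either response was bilateral. If they were not, the result can lie anywhere from 0/2 (both hemispheres required) to 2/2 (either counts).

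**6. Events available.** At the pilot rate of 2/10, expect 30 × 0.2 = 6 events in all, 20 × 0.2 = 4 of them among the new patients. For illustration, 5/6 detected has an exact 95% CI of 36% to 99.6%. An assumed AUC of 0.75 has a Hanley-McNeil SE of 0.124 for 6 v 24 (95% CI 0.51 to 0.99) and 0.153 for 4 v 16 (0.45 to 1.05, capped at 1.00).

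**The case against.** The best defence has four parts.

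*A comparison is implied.* The imaging is set against the neurological exam, and a correlation with future vasospasm needs patients both with and without it. The remark that no control group is needed can be read as declining a separate arm. This stands. A reader might infer that the plan lacks a reference standard, or means to look only at patients with vasospasm; the documents do not support either. What is missing from the visible text is the hemisphere rule and the measure.

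*Figures are not shown.* Two are missing from IRB Concerns, after the text on comparison methods, and the method text refers to slides. They may hold some of these rules. The slides are introduced as statistics on the data maps and percent change, which makes an association analysis there less likely but does not exclude it. So one cannot infer that the whole plan lacks the analysis.

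*The t-test text is largely retrospective.* It describes what was done in the pilot, and the pre/post sentence may only define the predictor. That is partly fair. But the pre/post sentence is written in the future tense and is the only stated statistical comparison.

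*This is a feasibility pilot.* Two events are said to preclude a firmer proposal, the scans do not guide care, and a formal study would follow. This lowers the severity. It excuses the absence of a power calculation, but not of a unit, a definition and a named measure, which can be set with few events.

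**Conclusion.** The concern holds as a gap to close before analysis, not as a flaw that defeats the study. The stated main aim and the one named test do not meet, and the two definitions of abnormal response give opposite labels to at least 3 of 20 pilot hemispheres. Under the 30% definition, at least 10 of 16 hemispheres without vasospasm are abnormal, so a consistent finding in vasospasm patients alone would not show prediction.

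These bounds come from 10 patients, rest on the two readings stated in the check, and are illustrative. A reader might infer that the pilot showed a sensitivity of 1/2; that holds only for the significant-rise definition with concordant hemispheres, and the text does not establish concordance. With about 6 events expected, prespecification will make the result interpretable but not precise.

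**What to change.** In IRB Concerns, keep the paired t-test as a description of drug response only. Before analysing the 20 further patients, state:

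1. one percent CBF change per patient, with the rule for combining hemispheres;
2. one definition of abnormal response for the analysis, reconciling the two now in the section;
3. a comparison of patients with and without symptomatic vasospasm by a named measure, for example an exact rank-sum test or AUC with 95% CI;
4. sensitivity and specificity with exact CIs.

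Show the first 10 patients, whose results are known, separately as well as pooled. Say that the estimates are imprecise and serve to inform a formal study. If the figures or slides already contain these rules, move them into the text.

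The cost is some wording and a few tables. Both scans and vasospasm status are already collected (Scan procedure; Information Collected from Medical Records), so no patients or procedures are added. Conclusions become more modest, and the estimate from the new patients alone, with about 4 events, will be very wide.
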